2.2. Sample size

This study used knee osteoarthritis severity as the primary outcome measure. Given the lack of prior research on the effect of patient navigation mode on patients' knee osteoarthritis severity. Therefore, the sample size calculation for the present study was based on the results of the pre-experiment, which showed an effect size of 0.8 on knee osteoarthritis severity. To achieve a statistical power of 0.80 and an alpha level of 0.05, a sample size of 33 participants per group is required. Considering a 20% attrition rate, the total estimated sample size is 84 participants, with 42 participants per group.

3. Randomization and blinding

A non-research team member randomly selected an initial starting point from a pre-generated computerised random number table. From this point, the corresponding random numbers were sequentially identified, ranging from 1 to 84. After sorting the random numbers, participants were randomly assigned in a 1:1 ratio to either Group 1 (the experimental group) or Group 2 (the control group). Group assignments were concealed within 84 consecutively numbered, identical, opaque, and sealed envelopes, which the non-research team member securely kept. On the day of participant enrolment, after completing demographic and clinical data collection, as well as baseline assessments, the principal researcher (recruiter) retrieved the envelope corresponding to the participant's sequential number from the custodian. The envelope was opened, and the participant was assigned to the designated group.

Due to the nature of the intervention, the experimental group received exercise guidance from navigator, while the control group did not. Consequently, blinding of participants, recruiters, or research intervention staff was not feasible. However, outcome assessors and data entry analysts will be blinded. The outcome assessor is an independent research assistant who remained unaware of the allocation status throughout the study. Before the

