- ② Guidance for participants with underlying conditions: Upon admission, navigators conduct detailed assessments of participants' underlying conditions, collaborating with the medical team to develop personalised management plans. Participants receive instruction on monitoring relevant indicators and operating associated devices, adhering to medication schedules as prescribed, managing daily lifestyle factors (diet, exercise, weight control), and recognising and handling emergencies or abnormal symptoms.
- ③ Postoperative self-management guidance for TKA:
 - Wound care: Explain dressing change schedules, precautions during dressing changes, and wound dressing observation.
 - Complication prevention: Instruct on preventing postoperative wound infections, deep vein thrombosis, and constipation.
 - Postoperative life precautions: Inform on prohibited movements, allowed actions, and mobility techniques.

5. Data collection

Data collection will be conducted at five time points: on admission day (baseline, T0), surgery day (preoperative) (T1), one week post-surgery (T2),

two weeks post-surgery (T3), and four weeks post-surgery (T4). The collected study data will include demographic and clinical information collected by the principal investigator (recruiter), as well as outcome measures collected by assessors from T0 through T4. These outcome indicators encompass knee osteoarthritis severity, exercise adherence, self-efficacy, knee joint function, knee range of motion, and pain intensity.

6. Outcome assessment

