Knee range of motion (ROM) will be measured with a goniometer. ROM measurement assesses knee movement amplitude, serving as a critical indicator of knee joint function and a key indicator for evaluating rehabilitation outcomes following total knee arthroplasty. Normal knee range of motion values are as follows: flexion, 0°–135°; extension, 0° (some individuals may exhibit hyperextension of 0°–10°); active range, 0°–135°; and passive range, up to 150°.

Pain intensity will be measured using the Visual Analogue Scale (VAS). The VAS consists of a 10-centimetre horizontal line divided into 10 equal intervals, where higher scores represent greater pain intensity. A score of 0 denotes no pain, whereas a score of 10 denotes the most severe pain imaginable. Patients are instructed to mark the point on the line corresponding to their perceived pain intensity.

7. Statistical analysis

IBM® SPSS Statistics 27.0 will be used to analyse the data from all randomised participants. Statistical significance was set at $p \leq 0.05$. Categorical variables (e.g., gender, marital status, payment type) appeared as frequencies and percentages. Continuous variables (e.g., age, height, weight) appeared as mean \pm standard deviation (SD). Continuous data meeting the assumptions of normality and homogeneity of variance were analysed using independent-sample t-tests; otherwise, the Wilcoxon signed-rank test appeared. Categorical data were analysed using the chi-square test or Fisher's exact test for intergroup comparisons. Generalised Estimating

Equations (GEE) were employed to compare longitudinal changes in outcome variables between groups, with statistical significance set at $p < 0.05$ (two-tailed). The GEE was chosen as it accounts for within-subject correlations inherent in repeated measures, thereby improving the efficiency of parameter estimation in longitudinal analyses. Moreover, the GEE approach flexibly accommodates missing data. When the proportion of missing data was below 5%, the GEE inherently accommodated the missing values; otherwise, multiple imputation procedures were applied.

8. Trial monitoring

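### Section 7 names a paired test, the Wilcoxon signed-rank test, as the fallback for the independent-sample t-test, although the two arms are unmatched

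*Combined protocol and SAP*

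**What the plan says.** The rule is in Section 7 (Statistical analysis). Its first half reads "Continuous data meeting the assumptions of normality and homogeneity of variance were analysed using independent-sample t-tests", and its second half "otherwise, the Wilcoxon signed-rank test appeared". The signed-rank test is therefore the direct substitute for a two-independent-sample test.

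The surrounding text indicates what the rule is for:

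- The sentence before it describes the summaries: "Continuous variables (e.g., age, height, weight) appeared as mean" with standard deviation.
- The sentence after it gives the categorical counterpart, chi-square or Fisher's "exact test for intergroup comparisons".
- The same paragraph then turns to GEE, which "were employed to compare longitudinal changes in outcome variables between groups".

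Section 1 describes two parallel groups. Section 3 describes 1:1 allocation of 84 participants from a random number list, with no matching. It places allocation "after completing demographic and clinical data collection, as well as baseline assessments".

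**The concern.** The signed-rank test ranks differences within pairs, or differences of single values from a fixed number. An independent-sample t-test compares two separate sets of people. One cannot stand in for the other unless patients are matched, and here they are not. No section describes a within-patient comparison that the signed-rank test might have been meant for, and none names the rank-sum test that would normally fill this place.

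At stake is whether a stated analysis rule can be followed. When a continuous variable fails the t-test assumptions, an analyst keeping to the text has to invent a pairing, run a test that answers another question, or depart from the plan.

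**Working it through.** **Inputs.** Arm sizes of 42 and 42, total 84 (Section 2.2). Unmatched 1:1 allocation (Section 3). Eligible age 45 to 90 years (Section 2.1). The rule, its examples and the role of GEE (Section 7). The plan gives no figure for this rule, so there is none to reproduce. The simulated data shapes below are assumptions.

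**1. Are there pairs?** Demographic, clinical and baseline data are taken once, before allocation. For a variable such as age there are 42 + 42 = 84 single values and 0 within-patient pairs.

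**2. What each test needs.**

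- Signed-rank: form d_i = x_i − y_i for each pair, rank |d_i|, and sum the ranks of the positive differences. With n = 42 pairs the null mean is n(n+1)/4 = 42 × 43/4 = 451.5. The index i must link one patient in each arm, and the design supplies no such link.
- Rank-sum: rank all 84 values together and sum the ranks of one arm. The null mean is 42 × 85/2 = 1,785. Only arm membership is needed, and the design supplies it.

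**3. Literal reading A: pair patients arbitrarily.** One simulated data set was drawn with 42 log-normal values per arm (log-SD 0.6, log-means 0 and 0.3). The rank-sum p-value was 0.037. The second arm was then re-ordered at random 2,000 times and the signed-rank test run each time. The p-values ranged from 0.003 to 0.21, with median 0.043, and 57.7% fell below 0.05. Nothing changed but row order. With 42 against 40 patients the Python routine returned an error, because the test has no use for unpaired patients. SPSS, the plan's software, was not tried.

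The long-run error rate is a separate matter. With no true difference, 42 per arm and patients paired in row order (40,000 simulated trials for each of four shapes: normal, exponential and two log-normal), signed-rank type I error was 0.049 to 0.051 and rank-sum 0.050 to 0.051. The two tests gave different verdicts at 0.05 in 2.7% to 3.7% of comparisons.

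**4. Literal reading B: test within each arm.** With one value per patient, the one-sample form against zero asks whether the median is 0. Every eligible age is positive, so the statistic takes its maximum, 42 × 43/2 = 903. The null variance is n(n+1)(2n+1)/24 = 42 × 43 × 85/24 = 6,396.25, so the SD is 79.98. Then z = (903 − 451.5)/79.98 = 5.65, which gives p below 0.0000001 in both arms whatever their ages. This says nothing about balance between arms.

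**5. How far the rule reaches.** The sentence says only continuous data and does not mention baseline. The examples beside it, and the separate assignment of longitudinal outcomes to GEE, point to baseline and descriptive comparisons. That is an inference. If the rule were used to compare one change score per patient between arms, the test would still be the wrong one, for the reason in step 1.

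**The case against.** The best defence is that this is a slip of name with no consequence. The test is offered in place of an independent-sample t-test, and the next sentence speaks of comparison between groups, so a competent analyst would run the rank-sum test. Baseline p-values in a randomised trial decide nothing about efficacy, and Section 7 does not use them to choose covariates, populations or models. Even row-order pairing keeps type I error near 0.05.

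Most of this stands, and it keeps the severity low. It does not justify leaving the text alone: these are different procedures, and the analysis section should name the one to be run.

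A reader might infer three stronger points that the documents do not support.

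- *That the primary outcome will be tested wrongly or lose power.* Section 7 gives longitudinal change in outcomes to GEE, and nothing in it directs the T0 to T1 change in WOMAC to the fallback.
- *That the fallback inflates false positives.* The figures in step 3 show that it does not under arbitrary pairing. The fault there is dependence on row order and some disagreement with the rank-sum test. The range 0.003 to 0.21 comes from one illustrative data set and is not an error rate.
- *That the slip obliges the sponsor to specify a particular GEE contrast for the primary outcome.* How fully Section 7 defines the primary analysis is a separate question, which this error does not settle.

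**Conclusion.** The rule is wrong as written; severity is minor. The named fallback does not fit two unmatched arms, and the document names no alternative that does. Followed literally, it gives a p-value that depends on row order and cannot use all patients when arm sizes differ, or it gives tests that do not compare the arms.

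The mismatch itself rests only on the wording of Section 7 and the design in Sections 1 and 3. The limited reach rests on reading the rule as mainly a baseline and descriptive one, which the context suggests but the sentence does not state. The numerical illustrations rest on assumed data shapes. No effect on the primary result or on any other efficacy conclusion is shown.

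**What to change.** In Section 7, replace the Wilcoxon signed-rank test with the Wilcoxon rank-sum (Mann-Whitney U) test as the fallback for between-group comparisons of continuous data. This changes one test name. It needs no extra patients, no change to the sample size and no change to trial conduct.

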2.1. Participant selection criteria

Inclusion Criteria: (i) patients diagnosed with knee osteoarthritis who are undergoing primary unilateral total knee arthroplasty; (ii) aged between 45 and 90 years; (iii) assessed by the attending physician as having sufficient physical capacity to tolerate preoperative rehabilitation exercises and adequate communication skills to cooperate with all examinations and assessments; and (iv) informed consent was obtained from the patient, and the signed informed consent form was duly completed.

Exclusion Criteria: (i) patients who are uncooperative due to impaired consciousness, cognitive dysfunction, or other factors; (ii) presence of severe concurrent comorbidities, including liver cirrhosis, respiratory failure, renal failure, malignancy, or trauma; (iii) a history of significant neuromuscular disorders or other joint diseases, as determined by the attending physician, that impair knee joint function; (iv) a time interval of greater than 7 days or less than 3 days between the admission day date and the scheduled surgery date; and (v) patients who have undergone systematic lower limb functional training within the past four weeks.

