6.1. Primary outcome

The primary outcome is the change in knee osteoarthritis severity from admission day (baseline, T0) to surgery day (preoperative) (T1). As the intervention in this study aims to enhance patient adherence to preoperative rehabilitation exercises, the ultimate objective is to improve their rehabilitation outcomes. Therefore, the change in knee osteoarthritis severity from T0 to T1 in both groups of participants will be used to evaluate the effectiveness of the intervention.

Knee osteoarthritis severity will be measured using the Chinese version of the Western Ontario and McMaster Universities Osteoarthritis Index (WOMAC) Scale, which is a self-administered instrument specifically developed to assess the severity of knee osteoarthritis and the efficacy of related treatments (Bellamy et al., 1988). The scale consists of 24 items divided into three subscales: pain (5 items), stiffness (2 items), and physical function (17 items). Several scoring methods have been developed for the Western Ontario and McMaster Universities Osteoarthritis Index Scale items (Noyes, 2016). In this study, a 5-point Likert scale is employed, where 0 represents “no difficulty” and 4 represents “extreme difficulty”. The total score ranges from 0 to 96, with higher scores reflecting more severe knee osteoarthritis.

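### Section 7 does not say how baseline WOMAC enters the GEE; adjusting the primary T1 contrast for T0 WOMAC is a nearly free and probably modest gain in precision.

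*Combined protocol and SAP*

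**What the plan says.** Section 6.1 defines the endpoint: "The primary outcome is the change in knee osteoarthritis severity from admission day (baseline, T0) to surgery day (preoperative) (T1". It adds that this change, compared across the two groups, is how effectiveness will be judged. Section 6.2 makes WOMAC change at T2, T3 and T4 secondary.

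Section 7 covers "all randomised participants" in effect, since the software "will be used to analyse the data from all randomised participants". For outcomes over time it says that GEE "were employed to compare longitudinal changes in outcome variables between groups", two-tailed at 0.05. It lists no model terms, working correlation, role for T0 or covariate. It neither plans baseline adjustment nor rules it out. It also names independent-sample t-tests for continuous data. The natural reading is that these describe baseline characteristics, but the text does not limit them to that use.

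Section 7 handles missing data as follows: "When the proportion of missing data was below 5%, the GEE inherently accommodated the missing values; otherwise, multiple imputation procedures were applied".

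Three other places bear on the point:
- Section 3: the allocation envelope is fetched "after completing demographic and clinical data collection, as well as baseline assessments".
- Section 2.2: the sample size rests on a pre-experiment "which showed an effect size of 0.8 on knee osteoarthritis severity", without saying which SD standardises it. It then says "Considering a 20% attrition rate, the total estimated sample size is 84 participants, with 42 participants per group".
- Section 2.1 excludes patients with "a time interval of greater than 7 days or less than 3 days between the admission day date and the scheduled surgery date", so T0 and T1 are 3 to 7 days apart.

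**The concern.** The endpoint is one contrast on a scale that is also measured before randomisation. Section 7 names a method family but leaves open how the baseline measurement is used, and that choice sets the precision of the primary result. With T0 as just another response level, the estimate is the raw difference in mean change. That subtracts the whole of each baseline score, even though part of the score's variation does not carry over to T1. Adjusting for T0 subtracts only the part that predicts T1.

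At stake is a confidence interval somewhat wider than the collected data allow, and a model statement that would otherwise be settled after the data exist. Bias is not at stake, because both analyses estimate the same arm difference under randomisation.

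**Working it through.** **Inputs from the documents.** Effect size 0.8, power 0.80, alpha 0.05, 33 per group, 20% attrition, 84 in total (section 2.2); two-tailed test (section 7).

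**Assumed.** The T0-T1 correlation ρ and the ratio of the T1 SD to the T0 SD (s1/s0). The documents give neither, so a range is shown.

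**The plan's own figures.** An effect of 0.8 with two-sided 0.05 and power 0.80 needs 25 per group (normal approximation) or 26 (t-test), not 33. The figure 33 matches power 0.90 (normal). The attrition step reproduces: 33/0.80 = 41.25, rounded up to 42 per group, 84 in total. Power at 33 per group with effect 0.8 is 89.3% (noncentral t), and 95.2% at 42. The mismatch at 33 is a separate matter; here it means only that the trial has power to spare for its own effect size.

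**What the planned GEE estimates if T0 is a response.** With arm, visit and arm-by-visit terms and complete data, the T1 contrast equals the difference in mean change. A fit to one simulated data set gave -0.1281 both ways.

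**Variances per participant.**
- Change score: s0² + s1² − 2ρ·s0·s1
- Adjusted for T0: s1²(1 − ρ²)
- Their difference is (s0 − ρ·s1)², which is never negative. Before the cost of estimating the covariate, adjustment therefore cannot lose. The gain is nil only when ρ·s1 = s0.
- With s0 = s1 the ratio, adjusted to change, is (1 + ρ)/2.

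**Cost of the covariate.** The variance is multiplied by 1 + 1/(2n − 4), which is 1 + 1/62 = 1.0161 at n = 33. The t quantile goes from 1.99773 (64 df) to 1.99834 (63 df). Example at ρ = 0.7 with equal SDs: √(0.85 × 1.0161) × 1.99834/1.99773 = 0.930, a CI 7% narrower.

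**Results at 33 per arm, cost included.** The CI columns give adjusted width divided by change-score width. The power column takes 0.8 in SDs of change, against 89.3% unadjusted.

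| ρ | CI, s1/s0 = 1 | CI, s1/s0 = 0.8 | CI, s1/s0 = 1.25 | Adjusted power, s1/s0 = 1 |
|---|---|---|---|---|
| 0.3 | 0.813 | 0.714 | 0.893 | 97.6% |
| 0.5 | 0.873 | 0.762 | 0.953 | 95.6% |
| 0.7 | 0.930 | 0.799 | 0.999 | 93.1% |
| 0.8 | 0.957 | 0.807 | 1.008 | 91.7% |
| 0.9 | 0.983 | 0.786 | 0.983 | 90.3% |

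The worst cell is s1/s0 = 1.25 with ρ = 0.8, where ρ·s1 = s0 exactly and only the cost remains. The CI is 0.8% wider and power is 88.8% against 89.3%. At 42 per arm the equal-SD ratios for ρ = 0.5 to 0.9 are 0.872, 0.928, 0.955 and 0.981, and the worst cell is 1.006.

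**Check of the proposed model.** In a GEE on T1-T4 with arm-by-visit and T0-by-visit terms, each visit has its own intercept, arm effect and T0 slope. With complete data the T1 arm estimate is then the ANCOVA estimate at T1. A fit to a simulated set of 84 confirmed this under independence and exchangeable working correlations. The CI ratios above use ordinary regression standard errors, so robust GEE standard errors will differ slightly.

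**The case against.** The strongest reply is that little is missing. Section 6.1 fixes the scale and interval, and section 7 compares longitudinal changes between groups. Read together, they point to the arm difference in T0-T1 WOMAC change. This stands. A reader might infer that the primary contrast is undefined and open to any test, such as a group main effect or a joint test over all visits. The documents do not support that: a main effect does not compare changes, and section 6.2 makes the later visits secondary. What is missing on the contrast itself is model notation.

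A second reply is that adjustment is a preference, since a change-score contrast is valid and the gain may be small. The first half stands. On size, a 3 to 7 day interval makes a high ρ plausible, and at 0.7 to 0.9 with equal SDs the gain is only 7% to 2%. If the T1 SD is 1.25 times the T0 SD, it is about nil at ρ 0.7 and 0.8. The suggestion survives because it costs almost nothing and cannot lose more than about 0.8% of CI width under these assumptions.

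A third reply is that moving to ANCOVA would leave GEE and so need its own missing-data rule. That is a good reason to put T0 into the planned GEE instead.

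**Conclusion.** The point holds as a low-cost improvement with a small prespecification element. Section 7 should say how T0 enters, and adjustment is the better choice. Under assumed ρ of 0.5 to 0.9 and equal SDs, the CI at 33 per arm is about 13% to 2% narrower, with the smaller gains the more plausible. The gain is larger if the T1 SD is below the T0 SD.

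A reader might go further and infer that the unadjusted analysis is wrong or leaves the trial underpowered. The documents do not support that. With 0.8 in SDs of change, unadjusted power is 89.3% at 33 per arm. If 0.8 were instead in T1 SDs, unadjusted power would fall below 80% only in low-ρ cells of the range tried:
- equal SDs: 77.2% (ρ 0.3, 33 per arm);
- T1 SD 0.8 times the T0 SD: 66.2% and 79.8% (ρ 0.3 and 0.5, 33 per arm) and 76.8% (ρ 0.3, 42 per arm).

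Section 2.2 does not say which SD applies, and nothing in the documents indicates so low a ρ.

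**What to change.** In section 7, state the primary analysis:
- a GEE in all randomised participants, with WOMAC at T1-T4 as the response;
- terms for arm, visit, arm-by-visit, T0 WOMAC and T0-by-visit;
- one primary test, the arm contrast at T1, two-sided 0.05, reported with a 95% CI;
- arm contrasts at T2-T4 labelled secondary.

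The existing missing-data rule can stay as it is, because the method remains GEE.

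The cost is a few sentences of SAP text and one more covariate to estimate at T1. No visit, form or participant is added, and the sample size does not change. At worst, at 33 per arm, the CI is about 0.8% wider and power about 0.5 points lower.

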study, the principal researcher (recruiter) trained the outcome assessor. The outcome assessor independently assessed outcomes and collected data for both groups from T0 to T4. Moreover, the principal researcher (recruiter) instructed all participants not to disclose their group assignment to the outcome assessor. Furthermore, two research assistants, who were not involved in the study process, served as data entry analysts. The group assignment was concealed from these analysts by using coded group identifiers (Group 1 and Group 2) to ensure blinding.

4. Intervention

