The Clinical Research Management Department and the Ethics Committee of the study-conducting hospital will oversee trial implementation and ensure compliance with ethical standards. The principal researcher is required to submit regular progress reports and interim results to the Clinical Research Management Department and the Ethics Committee of the study-conducting hospital. They will review the completeness, accuracy, and timeliness of data collection, as well as procedures related to participant enrolment, informed consent, eligibility assessment, and protocol adherence. Based on the findings of interim reports and a comprehensive evaluation of the study's efficacy, safety, and feasibility, they will make the final determination regarding whether the trial should be terminated.

9. Ethical

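### Section 8 lets efficacy enter the termination decision without excluding or bounding a stop for benefit, so the plan does not secure its 5% type I error

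*Combined protocol and SAP*

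**What the plan says.** **Monitoring (Section 8).** The principal researcher must "submit regular progress reports and interim results to the Clinical Research Management Department and the Ethics Committee". The review that is itemised is administrative: "They will review the completeness, accuracy, and timeliness of data collection", followed by enrolment, consent, eligibility and adherence. The termination sentence goes further. It rests on interim reports and on an evaluation of "efficacy, safety, and feasibility, they will make the final determination regarding whether the trial should be terminated", where the pronoun refers to the two oversight bodies.

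**Analysis (Section 7).** The software "will be used to analyse the data from all randomised participants". Generalised estimating equations (GEE) compare "longitudinal changes in outcome variables between groups, with statistical significance set at $p < 0.05$ (two-tailed"). No interim test, boundary or alpha spending is described.

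**Sample size (Section 2.2).** "To achieve a statistical power of 0.80 and an alpha level of 0.05, a sample size of 33 participants per group is required". There is no allowance for interim looks.

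**Blinding (Section 3), for the minor point.** Participants are allocated to "Group 1 (the experimental group) or Group 2 (the control group"). The same two labels are then the codes meant to blind the analysts: "two research assistants, who were not involved in the study process, served as data entry analysts".

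**The concern.** A test at 0.05 has a 5% false-positive rate if it is done once. If accumulating efficacy data can also end the trial with a claim of benefit, each look is a further chance of a false positive. Unless a boundary allows for this, the overall rate exceeds 5%, and the estimate at an early stop tends to overstate the effect.

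Early looks are practicable here. The primary outcome is the change in WOMAC from admission (T0) to the day of surgery (T1), and Section 2.1 excludes intervals shorter than 3 or longer than 7 days. Primary data therefore exist within about a week of each enrolment. The interim results are also submitted by the principal researcher, who as recruiter is not blinded (Section 3). Discretion that is left undefined matters more in that setting.

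At stake is whether a reader of the final report can confirm the error rate of the primary test.

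The minor point has no bearing on type I error. Coded labels protect analysis choices only if the analysts cannot look up the key, and Section 3 prints it.

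**Working it through.** **Inputs.** Alpha 0.05, power 0.80, effect size 0.8, 33 per group, 20% attrition, 84 in total (Section 2.2); two-sided testing (Section 7, stated for the GEE). The documents give no number or timing of looks. One look at half information is my assumption, used only for illustration.

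**1. The plan's own figures.**
- A single two-sided test at |Z| > 1.960 has error 2 × [1 − Φ(1.960)] = 0.050. The stated alpha is right for one look.
- Attrition: 33 / (1 − 0.20) = 41.25, rounded up to 42 per group, or 84. This reproduces.
- 33 per group at 80% power: 2 × (1.960 + 0.842)² / 0.8² = 24.5, so 25 per group (26 with the t-test). This does not reproduce. The mismatch is a separate matter and does not affect this point.

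**2. Illustration: one look at half information, both tests at 0.05.** With no true effect, Z₁ and Z₂ are standard normal with correlation √0.5 = 0.707.
- Error = 1 − P(|Z₁| ≤ 1.960 and |Z₂| ≤ 1.960) = 0.0831.
- Of this, 0.0500 arises at the interim look and 0.0831 − 0.0500 = 0.0331 at the final test alone.
- Check by simulation (400,000 null trials, two-sample t-tests, 42 per group, look at 21 per group): 0.0835, against 0.0496 with no look.

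**3. The same look with an O'Brien-Fleming boundary.** Set c₁ = c√2 and c₂ = c, and solve 1 − P(|Z₁| ≤ c₁ and |Z₂| ≤ c₂) = 0.05.
- c = 1.977, so c₁ = 2.797.
- Nominal two-sided p: 0.0052 at the interim, 0.0480 at the end.
- Simulated error with t-tests: 0.0499.

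**4. Power cost of that boundary at effect size 0.8 and 33 per group.** Drift = 0.8 × √(33/2) = 3.250.
- No look: Φ(3.250 − 1.960) = 0.901.
- O'Brien-Fleming, look at information fraction 0.5: 0.899.
- Difference: about 0.2 percentage points. With simulated t-tests: 0.8922 to 0.8899, again about 0.2.

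**5. Where a limit could have been set.** Section 8 names efficacy and gives no rule. Section 7 gives one threshold and no interim test. Section 2.2 assumes a single test. No other section addresses stopping the trial; Section 9.1 covers withdrawal of individual participants only.

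**6. Minor point.** One paragraph of Section 3 equates Group 1 with the experimental arm and Group 2 with control. A later paragraph uses those names as the blinding codes. Anyone who has read the section can decode the file.

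**The case against.** The strongest reply is that Section 8 is general oversight wording and that one final analysis is intended. The itemised review is administrative, Section 7 analyses all randomised participants and describes no interim test, and 84 numbered envelopes are prepared. The termination decision is described as an overall evaluation, not as a significance trigger. This is a fair reading and may be what is meant. It does not close the gap, because the text names efficacy as a ground for termination and nothing confirms the narrower intent. If that is the intent, a sentence settles it.

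A reader might infer that the type I error is inflated. The documents do not support that. They plan no efficacy stop, and efficacy-based stopping could be for lack of effect only, which would lower the error. The 8.3% depends on an assumed rule.

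A further objection is that, even with no interim look, 5% is not exact. Section 7 lists t-tests, a Wilcoxon test and GEE without saying which one tests the primary outcome, and an uncorrected robust GEE test can exceed 5% in samples of this size. That stands. The claim for the fix is therefore only that interim monitoring would not raise the error of the final test.

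On the codes, a reader might infer that the analysts are unblinded. That is not shown: they are described as outside the study process, and whether they have read Section 3 is not stated. The risk is real and the failure is not demonstrated.

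**Conclusion.** The point holds as a gap in the plan. As written, Section 8 permits termination on grounds that include efficacy, with no exclusion of a benefit stop and no boundary, alongside a final test that spends the whole 0.05. The 5% error is not secured, and the size of any departure cannot be fixed from the documents. The 8.3% assumes one look at half information, both tests at two-sided 0.05, and a stop whenever the first is significant.

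The correction should be made because it is nearly free and concerns the primary test. Confidence is moderate, since a single final analysis may be what is intended. The coding of the groups is a separate minor weakness in blinding.

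**What to change.** **Main option.** With the agreement of the two oversight bodies, state in Section 8 that the trial will not be stopped for benefit and that interim reports contain no between-arm comparison of efficacy. By-arm safety review continues unchanged, and the final threshold stays at 0.05.

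**If a benefit look is wanted.** Pre-specify one look at the T0–T1 WOMAC change when half of the planned participants (42 of 84) have T1 data, using the O'Brien-Fleming values from step 3 of the working. Those p values apply to a look at half information. Section 7 should carry the same final threshold.

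**Cost.** Two or three sentences and the bodies' agreement, which is needed because Section 8 assigns them the evaluation of efficacy. The main option gives up an unrestricted efficacy-based stop. The alternative costs the small loss of power in step 4.

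**Minor point.** In the analysis file, replace Group 1 and Group 2 by neutral codes mapped to the arms at random. The existing envelope custodian, who is outside the research team, should hold the key until the analysis is complete. The cost is one relabelled column.
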